2.1 Data analysis general information

Novartis will perform the primary and final analyses.

Analyses will be based on this document and performed using SAS® Version 9.4 (SAS Institute, Inc., Cary, NC) or later.

Categorical data will be presented as frequencies and percentages. For continuous data, the number of non-missing observations, mean, standard deviation, median, minimum, and maximum will be presented. For selected parameters, 25th and 75th percentiles may also be presented. Summary tables will be presented by visit when applicable.

All efficacy endpoints will be summarized descriptively using observed values and change from baseline at each visit, in addition to the analyses mentioned in the respective sections below.

The analysis will be primarily focused on period 1. However, subject disposition, study treatment exposure and prednisolone exposure will be also summarized for period 2. All safety analyses will also be performed for subjects who received OAV101 during either period 1 or period 2.

2.1.1 General definitions

Study treatment is OAV101 (1.2x10¹⁴ vector genomes) or sham administration.

The **date of first administration of study treatment** is defined as the date of OAV101/sham administration during Treatment Period 1.

The **date of second administration of study treatment** is defined as the date of OAV101/sham administration during Treatment Period 2.

Study day is the number of days since the date of first administration of study treatment for period 1 and number of days since the date of second administration of study treatment for period 2.

- Study day 1 is the date of the first administration of study treatment during Treatment Period 1 and the date of second administration of study treatment during Treatment Period 2 .
- Study day of date X = date X – date of first administration of study treatment during Treatment Period 1 + 1 if date X is on or after the date of first administration of study treatment during Treatment Period 1.
- Study day of date X = date X – date of first administration of study treatment during Treatment Period 1 if date X is before the date of first administration of study treatment during Treatment Period 1. Study days before the first study treatment administration during Treatment Period 1 will have the prefix “-”.

Baseline is defined as follows:

- **HFMSE**: Baseline value for HFMSE (i.e., total or individual item) score is defined as the average of HFMSE (i.e., total or individual item) score used for stratification (maximum of all available values before baseline visit) and the measurement or evaluation made at the baseline visit prior to the first administration of study treatment during Treatment Period 1, assuming both values have complete and valid scores available. If just one of the above mentioned values (score used for stratification and baseline visit measurement) has a complete and valid score available, then the baseline HFMSE (i.e., total or individual item) score is defined as the single available value.
- **RULM**: Baseline value for RULM total score is defined as the average of all non-missing assessments prior to the first administration of study treatment during Treatment Period 1, assuming all assessments have complete and valid total scores available. If two of the assessments have a complete and valid total score available, then the baseline RULM total score is defined as average of the two available assessment scores. If just one of the assessments has a complete and valid total score available, then the baseline RULM total score is defined as the single total score available.
- **Other assessments**: The latest non-missing measurement or evaluation made prior to the first administration of study treatment during Treatment Period 1.

Change from baseline is defined as post-baseline value minus baseline value.

For HFMSE and RULM, the **End of Follow-up Period 1** assessment is defined as the average of the Week 48 and Week 52 assessments, assuming both assessments have complete and valid total / individual scores available. If just one of the assessments collected at these two visits has a complete and valid total / individual score available, then the end of Follow-up Period 1

assessment is defined as the single assessment total / individual score collected at Week 48 or Week 52.

Last participation day can be calculated using end of participation date – date of second administration of study treatment + 1.

Inexact values will be handled as follows.

- If a laboratory value is recorded/reported as “>X”, “≥X”, “- If an antibody titer value is reported as <12.5, a value of 0.5×12.5 will be used and if ≥ 819200 is reported, a value of 1.5×819200 will be used for analysis purposes. The originally recorded values will be displayed in corresponding listings.

An **Adverse Event** (AE) is any untoward medical occurrence in a clinical investigation participant, which does not necessarily have a causal relationship with the drug or device under study.

A Treatment Emergent Adverse Event (TEAE) is any AE whose onset or worsening occurred after dosing on Day 1 till the end of follow-up period 2.

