to 5 year old age group from this natural history study were able to sit but not walk at baseline which was similar to the clinical features of the CL-102 participants. The 12-month HFMSE change from baseline in this 2 to 5 year old natural history group demonstrated a mean \pm standard deviation of 0.40 ± 4.09 (Coratti et al 2020b).

Review of the LS mean at various points in the study confirmed the importance of following the participants for 52 weeks to evaluate the statistical significance and clinical meaningfulness of the observed changes. Data analysis at time points before 52 weeks may not have sufficient power to adequately evaluate therapeutic efficacy.

b. Late onset SMA patient natural history supports a trial duration of 12 months for appropriate assessment of change from baseline in motor function (Coratti et al 2020a, Coratti et al 2020b).

In the largest and most comprehensive natural history study to date in 267 Type 2 SMA patients (age range 30 months to 33.4 years), the detailed data based on 652 assessments allows delineation of age groups based on disease progression as well as patient motor abilities (Coratti et al 2020b, Coratti et al 2020a). Of the 652 assessments, 541 were from patients who could sit but were never ambulatory and all but one patient had 2 to 4 *SMN2* copies. These key clinical features are aligned with the study population inclusion criteria for COAV101B12301. Although patient motor function declined with age in this natural history study, 12 months of assessment allowed clear characterization of changes across the age range, further supporting the 12-month trial duration chosen for the COAV101B12301 study population.

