- Obtaining a complete HFMSE assessment that is a true representation of the participant's motor ability is critical in order to appropriately investigate OAV101 efficacy. The completeness of the HFMSE assessment has been considered in Type 2 SMA motor assessment analyses, thus allowing for fair and valid assessment of motor abilities (Mercuri et al 2019, Coratti et al 2020b). Every effort should be made to administer all scale items appropriately following scale criteria. In the event that an item is not able to be administered, a 'Cannot Test' (CNT) is marked for that item. To ensure the patient's true motor ability is being represented, rescheduling of the assessment administration is warranted when any factor significantly impedes the participant's ability to perform the motor assessment which includes behavior issues (e.g., tantrums, inconsolable), refusal to participate in testing, transient pain, fractures, intercurrent surgery, or recent pneumonia or other infections. **CCI** [REDACTED]

[REDACTED] Study specific requirements around HFMSE administration requirements are outlined below. Based on prior experience in the open label AVXS-101-CL-102 clinical trial of intrathecal OAV101, very few incomplete assessments are anticipated.

Contractures: It is important to note that contractures alone do not exclude participants from being scored on the HFMSE. The impact of contractures on some assessment items needs to be established, therefore the therapist should indicate "limited by contracture". However, participants with severe contractures, which limit their ability to be positioned in prone during Screening, are not eligible (exclusion criterion 13).

HFMSE at Screening

- In order to assess trial eligibility, an HFMSE assessment with total score must be obtained during the Screening period ([Section 5.1](#)).
- Two HFMSE assessments are performed during the screening period. Although two complete HFMSE assessments is preferred at Screening, a minimum of one assessment with total score must be obtained.
- Rescheduling of the assessment administration within the screening window is required if an HFMSE assessment with a total score is unable to be obtained.

HFMSE assessment at baseline and post-OAV101 administration/sham procedure to Week 64 (End of Study)

- HFMSE is administered at each visit specified in the Schedule of Assessments ([Table 8-1](#)).

HFMSE assessment **CCI** [REDACTED]

[REDACTED]
[REDACTED]
[REDACTED]
[REDACTED]
[REDACTED]

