2.5.2 Statistical hypothesis, model, and method of analysis

The aim is to estimate the treatment effect of IT OAV101 compared to the sham procedure, for the target population on the primary endpoint. The justification of the corresponding primary estimand is detailed in [Section 1.2.1](#) of this SAP.

The statistical hypothesis for the primary endpoint being tested is that there is no difference in the change from Baseline in HFMSE total score at the end of Follow-up Period 1 in the OAV101 treatment group compared to the sham procedure group.

Let p_j denote the change from Baseline in HFMSE total score at the end of Follow-up Period 1 for treatments j , $j=0, 1$ where:

- 0 corresponds to sham procedure
- 1 corresponds to OAV101

In statistical terms, $H_0: p_1=p_0$, $H_A: p_1 \neq p_0$, i.e.:

- H_0 : OAV101 is not different from sham procedure with respect to the change from Baseline in HFMSE total score at the end of Follow-up Period 1.
- H_A : OAV101 is different from sham procedure with respect to the change from Baseline in HFMSE total score at the end of Follow-up Period 1.

The primary efficacy endpoint variable will be analyzed using a linear mixed effects repeated measures model (MMRM) with the observed change from Baseline in HFMSE total score at all post-Baseline visits (through the end of Follow-up Period 1) as the dependent variable. The fixed effects will include treatment, scheduled visit, treatment by visit interaction, CCI [REDACTED]

[REDACTED]. The primary analysis will be based on the FAS. An unstructured covariance matrix will be used. LSMs for each treatment group, standard errors, and associated 95% confidence intervals (CIs), difference of LSMs compared to sham procedure group, and the associated 95% CI for the difference, as well as the two-sided p-values will be tabulated by visit. The null hypothesis will be rejected if the two-sided p-value for the LSM difference between the OAV101 arm and the sham procedure at the end of Follow-up Period 1 is less than the alpha level dictated by the sequential testing procedure ([Figure 2-1](#)).

A line plot will be produced to display the LSMs for each treatment group and associated 95% CIs at each visit through the end of Follow-up Period 1.

In case of non-convergence issues, the covariance matrix will be simplified and a compound symmetry (CS) matrix will be used instead of the originally planned unstructured covariance matrix.

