2.6.2 Statistical hypothesis, model, and method of analysis

The continuous secondary endpoints of change from baseline in HFMSE and RULM scores in the younger age group or the whole study population will be analyzed in a similar manner to how the primary endpoint will be analyzed. The continuous HFMSE endpoint will include baseline HFMSE total score as a covariate in the model and the continuous RULM endpoints will include baseline RULM total score as a covariate in the model. Line plots will be produced for each of the continuous secondary endpoints to display the LSMS for each treatment group and associated 95% CIs at each visit through the end of Follow-up Period 1.

The dichotomous endpoint (proportion of responders, defined as participants who achieve at least a 3-point improvement from baseline in HFMSE total score at the end of Follow-up Period 1) will be analyzed by a Generalized Linear Mixed Effects model including treatment, CCI

[figure not shown]
The model will include “logistic” as the link function with unstructured (UN) covariance matrix.

In case of non-convergence of the above model, the endpoint will still be analyzed by a Generalized Linear Mixed Effects model with the covariance matrix changed to compound symmetry (CS). In case the model does not converge even then, the dichotomous endpoint will be analyzed by a logistic regression model including treatment, strata and the baseline HFMSE total score as covariate (if quasi-complete separation issue like 0 responders in sham group is encountered, “firth” correction will be applied to obtain the odds ratio, 95% CI and corresponding p-value). In this case, the proportion of responders and corresponding 95% CIs at each visit will be displayed and the odds ratio of OAV101 compared to sham group with associated 95% CIs and two-sided p-values will be provided for the End of Follow-up Period 1.

In all cases, estimates (difference or odds ratio) of OAV101 arm compared to sham group with associated 95% CIs and two-sided p-values will be provided.

Testing Procedure

CCI

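### Does putting the screening maximum into the HFMSE baseline distort the results enough to need a second baseline display?

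*SAP*

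**What the plan says.** SAP 2.1.1 sets the HFMSE baseline to the average of the "score used for stratification (maximum of all available values before baseline visit) and the measurement or evaluation made at the baseline visit". If only one of these two components is complete and valid, it stands alone. SAP 1.1 confirms that the stratification score is the highest from Screening Visits 1 and 2. Protocol 8.3.1.1 plans two screening assessments, requires at least one with a total score, and says that "very few incomplete assessments are anticipated". A maximum of two is therefore the usual case.

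Neither of the neighbouring definitions in SAP 2.1.1 uses a maximum. For the upper-limb scale, "Baseline value for RULM total score is defined as the average of all non-missing assessments prior to the first administration of study treatment". For the end of Follow-up Period 1, the "assessment is defined as the average of the Week 48 and Week 52 assessments".

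The change scores feed three kinds of output:

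- **Model-based, by arm and visit.** SAP 2.5.2: "A line plot will be produced to display the LSMs for each treatment group and associated 95% CIs at each visit". SAP 2.6.2: "Line plots will be produced for each of the continuous secondary endpoints to display the LSMS for each treatment group".
- **Descriptive.** SAP 2.1: "All efficacy endpoints will be summarized descriptively using observed values and change from baseline at each visit".
- **Responders.** SAP 2.6.1 applies a fixed 3-point cut to the HFMSE change, overall and at age 2 to <5 years.

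**The concern.** The larger of two error-prone measurements overstates the true value on average. Half of that overstatement enters the HFMSE baseline, and nothing comparable enters the later scores. A child whose motor function has not moved would show a small expected loss from the first HFMSE visit, Week 4, onward.

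Two readings could suffer. First, the planned Week 4 point and its 95% CI could suggest a motor decline after dosing that did not occur, while the RULM plots would carry no such offset. Second, the offset is of the same order as the untreated change that Protocol 4.2 cites: "The 12-month HFMSE change from baseline in this 2 to 5 year old natural history group demonstrated a mean" of 0.40 (SD 4.09). A reader who sets the sham arm against that figure could see a gain turn into a loss. If the offset also reached the treatment comparison, the primary result would be at stake.

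**Working it through.** **The plan's own power figure.** Inputs from SAP Section 3: difference 3, SD 5, 75 vs 50, two-sided 5%. SE = 5 × √(1/75 + 1/50) = 0.913; 3/0.913 = 3.286; power = Φ(3.286 − 1.96) = 0.908 (0.903 with the noncentral t). The stated value of about 90% is reproduced.

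**Size of the offset.** Let s be the within-child test SD, with stable status and independent, equal-variance normal errors. The expected maximum of two errors is s/√π = 0.564s, and half weight gives 0.282s.

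- One screening score only: 0.
- Day -1 score missing, so that the maximum of two stands alone: 0.564s.
- Screening errors correlated at r: 0.5 × s × √((1 − r)/π), which is 0.20s at r = 0.5.

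The documents do not give s. I assume 1 to 2 points, hence 0.28 to 0.56. If the natural-history SD of 4.09 were all test error on two single tests, s would be at most 4.09/√2 = 2.89 and the offset at most 0.82.

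**Primary comparison.** ANCOVA was simulated with 75 vs 50, change SD 5 and 8,000 trials per setting, for s = 1, 2 and 2.89. With a true difference of 3 the SAP rule estimates 3.00 to 3.01. Type I error is 5.0 to 5.2%, and power is 0.89 to 0.90, against 0.90 to 0.91 with a plain average of the three pre-treatment scores. At s = 2 the arm means are −0.57 and 2.44 instead of 0.00 and 3.00: both move, the difference does not.

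**Responders.** P(change ≥ 3) = 1 − Φ((3 + 0.282s − mean)/5), with mean 3 for OAV101 and 0 for sham (the sham value is assumed).

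| s | OAV101 | Sham | Odds ratio | Power |
|---|---|---|---|---|
| 0 | 50.0% | 27.4% | 2.65 | 0.720 |
| 1 | 47.8% | 25.6% | 2.66 | 0.712 |
| 2 | 45.5% | 23.8% | 2.67 | 0.704 |
| 2.89 | 43.5% | 22.3% | 2.69 | 0.695 |

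In simulation, responder power falls from 0.725 to 0.700 at s = 2 and from 0.732 to 0.695 at s = 2.89. Type I error stays at about 5%. With integer scores the fall in percentages is smaller: 50.7/28.1% to 47.5/25.6% at s = 2. With the planning rates of 75% vs 13% at age 2 to <5 years, s = 2 gives about 71% vs 11%, and power stays above 99%.

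**Week 4 interval by arm.** With no true change in any child, the maximum of two errors has variance 0.682s². The variance of the change is then s² × [1 + (0.682 + 1)/4] = 1.420s², so SD = 1.192s. For 75 children SE = 0.138s and 0.282/0.138 = 2.05, so the chance that the interval lies wholly below zero is Φ(2.05 − 1.96), about 54%. For 50 children it is about 39%. If true change varies between children with SD s, the figures are about 35% and 25%; with SD 2s, about 18% and 13%. A simulation with baseline adjustment gives slightly lower values, and 1.9 to 2.9% under the plain average.

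**Is the plain average better?** Suppose scores rise once, by g, after Screening Visit 1 (practice), and then stay level.

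- g = 0.5s: expected maximum = 0.5s × Φ(0.354) + 1.414s × φ(0.354) = 0.849s. SAP baseline = (0.849 + 0.5)s/2 = 0.675s, so the offset is 0.5s − 0.675s = −0.17s. Plain average: 0.5s − (0 + 0.5 + 0.5)s/3 = +0.17s.
- g = 1s: SAP rule −0.10s; plain average +0.33s.

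If scores instead rise by 0.25s at every test, the maximum is 0.698s, the SAP baseline is (0.698 + 0.5)s/2 = 0.599s, and the expected Week 4 change is 0.75s − 0.599s = +0.15s. There is then no drop at all.

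**The case for a change.** The strongest case for acting is that the asymmetry is plain in the text, the usual child has two screening scores, and the remedy is cheap: a footnote and one extra descriptive display, using a rule the SAP already applies to RULM. Under stable status and independent errors, a Week 4 interval wholly below zero is far more frequent than it should be. Prespecifying an explanation before unblinding is tidier than offering one later.

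The mechanism stands, and so does the small effect on responder percentages. The rest is weaker.

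- The 54% figure needs identical true change in every child and fully independent errors. Protocol 8.3.1.1 asks for the same evaluator throughout, which makes independence doubtful. With error correlation 0.5 and 80% of children having two screening scores, the simulated figures are 8 to 19% (OAV101) and 7 to 14% (sham).
- These are single-visit calculations, not the planned MMRM.
- The possible sign change in the young sham arm is mostly noise. With 26 children and SD 4.09 the SE is 0.80, so a true mean of 0.40 is observed below zero about 31% of the time with no offset, and about 44% at s = 1.
- A footnote asserting a downward offset would state an assumption as fact.

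**Conclusion.** This is a fair trade-off, and changing it brings no demonstrated gain. The estimand's summary measure is the between-arm difference (SAP 1.2.1), and the test concerns that difference (SAP 2.5.2). An offset common to both randomized arms cancels there. The responder tests remain valid, at a cost of roughly 1 to 4 points of power under the planning inputs. The visible SAP plans no test of one arm against zero. Section 4 removes the analysis that borrowed natural-history data, so no formal external comparison depends on the arm-level change.

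The arm-level curves may sit 0.28 to 0.56 points low if s is 1 to 2, two screening scores are available, status is stable and errors are independent. The offset is smaller with correlated errors, and practice gains can cancel or reverse it. It understates absolute benefit rather than inflating it, and it appears in the sham curve beside the treated one. Summaries of observed post-baseline values, already planned in SAP 2.1, do not use the baseline rule and show the Week 4 to Week 52 course without it.

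A second baseline would add a competing set of numbers with no evidence that it is nearer the truth: at a practice gain of 0.5s the two rules err equally in opposite directions, and above that the SAP rule is closer. Authors of the study report can note the feature when describing the arm-level plot. Some endpoint text is redacted, so a stated rationale for the rule may exist.
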